Treatment of anemia of chronic disease with true iron deficiency in pregnancy

[name], [name], [name], [name]

Department of Obstetrics and Gynecology

University Hospital of Zurich

[name]

[name]

SWITZERLAND

[contact]

Email: [contact]

Study population and criteria

Fifty anemic pregnant women with moderate anemia were prospectively observed and treated in the Anemia clinic at the Department of Obstetrics, University Hospital Zurich. All patients had singleton pregnancies. All pregnant women fulfilled criteria of moderate iron deficiency anemia defined as hemoglobin between 8.0 and 9.9 g/dl and serum ferritin $<15 \mu\text{g/l}$. In all women, the analyses of a blood count, iron status, erythropoietin, cross reactive protein (CRP), folic acid and vitamin B₁₂ were conducted.

Primary endpoint was the assessment and comparison of the efficacy of anemia treatment in pregnant women with iron deficiency anemia and anemia of chronic disease with true iron deficiency.

Secondary endpoint was the target hemoglobin $\geq 10.5 \text{ g/dl}$.

Exclusion criteria were anemia of other etiology (i.e. vitamin B₁₂ deficiency, folic acid deficiency, hemoglobinopathy etc.), liver or kidney disease, and multiples. Women with mean corpuscular hemoglobin (MCH) $\leq 25 \text{ pg}$, mean corpuscular volume (MCV) $\leq 75 \text{ fl}$; and percentage of microcytic erythrocytes (MRC) $\geq 3\%$ were tested for hemoglobinopathies.

Flow cytometry was used to determine the total iron demand of erythropoiesis by measuring HRC, C_{HR}, and RDW. Iron deficiency anemia is defined as anemia with depleted iron stores and with elevated levels of HRC $>2.5\%$, decreased C_{HR} $<28 \text{ pg}$ and elevated RDW $>15\%$. In combination with the indicators of erythropoiesis (hemoglobin, red blood cells and hematocrit) as well as the indicators of iron household (serum ferritin and transferrin saturation), we identified anemia of chronic disease with reduced iron stores but with normal level of hypochromic erythrocytes (HRC $<2.5\%$), normal reticulocyte hemoglobin content (C_{HR} $>28 \text{ pg}$), normal red blood cell distribution width (RDW $<15\%$) and low serum EPO levels for the grade of anemia (serum EPO $<50 \text{ U/l}$ by Hb $<10 \text{ g/dl}$).

Laboratory assessment

Hb, red blood cells (RBC), hematocrit (HCT), MCV, MRC, HRC, RDW, CHr were measured using an ADVIA® hematology analyser system (Bayer Diagnostics, Leverkusen, Germany). MCH was automatically calculated from Hb and RBC. Iron status was assessed by chemiluminescence-immunoassay (ACS 190; Ciba/Corning Diagnostic Corp., Cleveland, OH) of serum ferritin, iron and transferrin. Transferrin saturation was calculated as $100 \times \text{iron}/2 \times \text{transferrin}$. Radioimmunoassay was performed to determine vitamin B₁₂, folic acid and the levels of serum EPO. CRP was assessed through immunoturbidimetry. The hematological parameters were checked twice a week in the anemia clinic and iron status once a week.

Therapy protocol

According to hemoglobin level at the start of the therapy, the women were either treated with intravenous iron and rhEPO or with intravenous iron only twice weekly as described elsewhere. Patients with an Hb level between 9.0 and 9.9 g/dl (33 patients) received 200 mg iron sucrose (VENOFER®, Vifor Int., St. Gallen, Switzerland) intravenously twice weekly. If response to therapy was poor (i.e. Hb increase <0.7 g/dl) after 2 weeks (13 patients), patients additionally received rhEPO (10,000 U EPREX®, Janssen-Cilag, Baar, Switzerland). This cut-off for adequate primary response we choose on the basis of our previous experience. Patients with an Hb between 8.0 and 8.9 g/dl (17 patients) received iron sucrose (Venofer) and rhEPO (Eprex) twice weekly from the start of therapy.

Sufficient overall response to therapy (the difference of baseline hemoglobin and after therapy) was defined as Hb increase >1.0 g/dl. The maximum total iron dose was 1,600 mg, therefore therapy was stopped if the maximal iron sucrose dose was administered, or target Hb > 10.5 g/dl was achieved.

Side-effects (hypotensive and hypertensive response, allergic reaction, thromboembolic complications) were registered.

Statistical analysis

All statistical analyses were performed using the statistic program STATA 8 (Stata Corporation College Station, TX). $P<0.05$ was considered statistically significant. Baseline characteristics were compared using Mann-Whitney and Chi-square tests when appropriate.

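### Does writing the 10.5 g/dl hemoglobin target as at-or-above for the endpoint but strictly above for stopping therapy undermine the secondary endpoint?

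*Combined protocol and SAP*

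**What the plan says.** The section on study population and criteria defines the endpoint: "Secondary endpoint was the target hemoglobin $\geq 10.5 \text{ g/dl". The therapy protocol gives two alternative grounds for ending treatment: "therapy was stopped if the maximal iron sucrose dose was administered, or target Hb > 10.5 g/dl was achieved". The iron limit is set just before: "The maximum total iron dose was 1,600 mg". Women starting at 9.0 to 9.9 g/dl (33 of them) "received 200 mg iron sucrose" at each of two infusions a week. The other 17, starting at 8.0 to 8.9 g/dl, had iron and rhEPO from the outset, and their iron dose per infusion is not restated.

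The therapy protocol also defines a separate response measure: "Sufficient overall response to therapy (the difference of baseline hemoglobin and after therapy) was defined as Hb increase >1.0 g/dl". It does not say when the after-therapy value was taken.

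**The concern.** The same number and the same word, target, appear in both places with different signs, and nothing explains the difference. A reader may reasonably suspect that one threshold was meant and that one sign is a slip.

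The value in question is also an ordinary one. Hemoglobin was checked twice a week, every woman started at or below 9.9 g/dl, and any woman reaching the target had to rise through this region. If hemoglobin was recorded to 0.1 g/dl, which is how the documents quote it, a reading of exactly 10.5 is unremarkable.

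Three things could be at stake: the count of women reaching the secondary endpoint, whether treatment ended or went on at 10.5, and, through the last measurement, the classification of overall response.

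**Working it through.** **Where the two rules differ.** The inputs are the two inequalities, evaluated in steps of 0.1 g/dl (a recording precision assumed from how the documents quote hemoglobin).

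| Recorded Hb (g/dl) | Endpoint, ≥ 10.5 | Hb stopping criterion, > 10.5 |
|---|---|---|
| 10.4 | not met | not met |
| 10.5 | met | not met |
| 10.6 | met | met |

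They part company at one value only. They are also nested: any value above 10.5 is at least 10.5, so nobody can stop on hemoglobin at a reading that fails the endpoint threshold.

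**Endpoint.** The documents give one inequality for the endpoint, so a reading of 10.5 meets it whichever sign governed stopping. A second count under the strict sign would tabulate a definition that the plan never gives to the endpoint.

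**Stopping.** In the 9.0 to 9.9 g/dl stratum the iron maximum is reached after 1,600 / 200 = 8 infusions, or 8 / 2 = 4 weeks. The last cumulative dose below it is 7 × 200 = 1,400 mg. The sign can therefore affect stopping only up to infusion 7; after infusion 8 treatment ends under either sign. No such bound can be given for the 8.0 to 8.9 g/dl stratum without its dose per infusion.

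**Overall response.** Assume the after-therapy value is the one at stopping, which the documents do not say. Stopping at exactly 10.5 then gives:

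- baseline 9.5: 10.5 − 9.5 = 1.0, not above 1.0;
- baseline 9.9: 10.5 − 9.9 = 0.6, not above 1.0;
- any baseline below 9.5: an increase above 1.0, hence sufficient.

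Continuing could move a woman to sufficient only from a baseline of 9.5 to 9.9. From 9.5 a later value of 10.6 would do it (10.6 − 9.5 = 1.1); from 9.9 it would take a later value above 9.9 + 1.0 = 10.9. The shift can also go the other way: from 9.4, stopping at 10.5 gives 1.1, but a later value of 10.4 gives 1.0, which is not sufficient. The direction is therefore not fixed, and the whole chain depends on the assumed timing.

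**The case for a change.** The strongest case for acting is that one sign governs an outcome and the other governs treatment, so the difference is more than typographic. An endpoint and a stopping rule may differ, but a plan that intends this should say so rather than call both the target. The remedy would cost one sentence and need no new data.

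Part of this stands. The wording is inconsistent, and the documents do not show whether one target was meant or whether a woman at 10.5 was treated further. Two possible explanations cannot be settled from what is available: the treatment is said to be described in another source, which might state the rule, and a bar under the sign could have been lost when the file was read. The second is only a possibility, since inclusive signs elsewhere in the text survived.

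The step from inconsistency to consequence does not stand. No section requires the endpoint and the stopping rule to coincide, and both work as written. The effect on overall response comes from the unstated timing of the after-therapy measurement, a separate gap that would remain if the signs agreed. If that value was taken at a fixed time, the sign would not select the measurement and could act only through additional treatment.

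**Conclusion.** No change to the plan follows. The disagreement is confined to a recorded value of exactly 10.5 g/dl, and within the 33 women starting at 9.0 to 9.9 g/dl it can affect stopping only before the eighth infusion. The number of women affected cannot be derived and may be zero. The endpoint threshold is unambiguous as written, neither sign is shown to be wrong, and no result is shown to be unsound.

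What remains is clerical: the two sections must be reconciled in wording, with a statement of which sign governed stopping. This review takes no position on which it should be. Reporting the endpoint under two readings would add nothing.

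The conclusion that the rules differ only at 10.5 needs no assumption. The remark that 10.5 is an ordinary reading assumes recording to 0.1 g/dl, and the response calculation assumes that the after-therapy value is the one at stopping.

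### Therapy can stop on a single Hb reading above 10.5 g/dl, and no separate end reading is defined, so chance high readings can count as target attainment and inflate the Hb rise

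*Combined protocol and SAP*

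**What the plan says.** - **Entry** (Study population and criteria): women had "moderate iron deficiency anemia defined as hemoglobin between 8.0 and 9.9 g/dl".
- **Regimen** (Therapy protocol, first sentence): "According to hemoglobin level at the start of the therapy, the women were either treated with intravenous iron and rhEPO or with intravenous iron only". The bands hold 33 women (9.0-9.9 g/dl) and 17 women (8.0-8.9 g/dl).
- **Monitoring** (Laboratory assessment): "The hematological parameters were checked twice a week in the anemia clinic and iron status once a week".
- **Stopping** (Therapy protocol): "The maximum total iron dose was 1,600 mg", and "therapy was stopped if the maximal iron sucrose dose was administered, or target Hb > 10.5 g/dl was achieved".
- **Response** (Therapy protocol): "Sufficient overall response to therapy (the difference of baseline hemoglobin and after therapy) was defined as Hb increase >1.0 g/dl".
- **Target** (Study population and criteria): "Secondary endpoint was the target hemoglobin", set there at 10.5 g/dl or more. The stopping rule requires more than 10.5.

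The plan does not date the end reading, set a fixed assessment time or require that a crossing be confirmed. It does not say whether the starting Hb is the same count that qualified the woman. The Statistical analysis section names tests for baseline characteristics only.

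**The concern.** A woman has up to about 8 chances to record a value above 10.5, and one is enough to stop therapy. If that same count is her end value, it has been picked because it was high. Part of its height is reading-to-reading scatter, which then passes into both target attainment and the baseline-to-end rise.

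A second, less certain contribution comes from the start. All recorded starting values lie inside the entry window. If most women in the source population have higher Hb, a value inside the window tends to be a low reading for that woman and would drift up without treatment.

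The primary endpoint includes an assessment of efficacy, and there is no untreated control against which such errors could cancel. The target is a named secondary endpoint. What is at stake is an overstated rise and a target rate that includes women whose usual Hb is still below the line.

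**Working it through.** **Figures from the plan**
- Starting values: 33 + 17 = 50, so all lie within 8.0-9.9.
- Readings: 1,600 mg / 200 mg = 8 infusions. At two a week this is about 4 weeks and about 8 counts. The 200 mg dose is stated for the 9.0-9.9 band and assumed for the other.
- Poor response at 2 weeks (rise below 0.7): 13/33 = 39%.

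The plan gives no response rate, variance or power figure to reproduce.

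**Assumptions not in the documents**
- Single-reading within-woman SD of 0.2 or 0.3 g/dl, with 0.1 as a low case.
- True 2-week rise with mean 0.85 and SD 0.4. This puts roughly a third of women below 0.7 at 2 weeks, somewhat under the plan's 39%.
- Source-population Hb with mean 11.5 (SD 1.1), 10.5 (SD 1.0) or 9.5 (SD 0.8).
- No rhEPO add-on.
- Stop at the first reading above 10.5, otherwise at reading 8.

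**Formula**

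Overstatement of rise = (true start − recorded start) + (recorded end − true end).

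**Simulated women starting at 9.0-9.9, source mean 11.5**

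| | SD 0.2 | SD 0.3 |
|---|---|---|
| Start reading low by | 0.06 | 0.13 |
| End reading high by | 0.12 | 0.21 |
| Observed rise | 1.07 | 1.14 |
| True rise | 0.89 | 0.79 |
| Overstatement | 0.18 | 0.35 |
| Rise >1.0, observed vs true | 51% vs 39% | 59% vs 31% |
| Stopped at target, truly below 10.5 | 27% | 39% |

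The two parts add up: 0.06 + 0.12 = 0.18, and 0.13 + 0.21 = 0.34, which is 0.35 up to rounding.

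**Sensitivity to the source population**
- Mean 10.5: overstatement 0.15 (SD 0.2) to 0.29 (SD 0.3), with 27-40% of those stopped at target truly below 10.5.
- Mean 9.5: the start error almost vanishes (0.003-0.006). The overstatement is about 0.11-0.20, nearly all from the end reading.
- Across all three, the end reading is 0.10-0.21 too high and 27-41% of those stopped at target are truly below it. The error at the end is therefore stable, and the error at the start is not (near 0 to about 0.14).
- SD 0.1: overstatement about 0.05, rise >1.0 in 44% observed and 44% true, and about 10% of those stopped at target truly below 10.5.

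**Women starting at 8.0-8.9** (source mean 11.5, same slopes): the end reading is high by 0.05-0.12. Rise >1.0 is 81% observed vs 81% true (SD 0.2) and 83% vs 77% (SD 0.3). About half reach the dose cap.

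**Repeated looks alone.** Take no true change, source mean 10.5 (SD 1.0) and women from the whole 8.0-9.9 window. Counting any crossing in 8 readings gives false target attainment of 1.3%, 9.0% and 20.6% at SD 0.2, 0.3 and 0.4. One reading at a fixed week 4 gives 0.2%, 2.0% and 5.2%.

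**Check of the remedy.** The true weekly slope was 0.428 (SD 0.2) and 0.416 (SD 0.3). A mixed model on all counts gave 0.421 and 0.404. Last minus baseline, divided by time, gave 0.57 and 0.77. With 50 women and SD 0.25 (120 runs), the truth was 0.425, the mixed model gave 0.429 and the simple difference 0.649.

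**The case against.** **The readings are undefined.** The text does not say that the triggering count is the end value or that the qualifying count is the baseline, and it refers elsewhere for regimen detail. This stands, and the point is therefore conditional on the natural reading. The same silence is a reason to define both readings.

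**Not every end reading is selected upward.** A reader might infer that every woman's rise runs between two readings picked by chance. The documents do not support that. The dose cap is a second way to stop, and a reading taken there has not been picked for being high. The entry window also has a lower limit, so the 33 + 17 = 50 count does not by itself show that starting values are selected low.

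**Stopping can work against the >1.0 response.** From a baseline of 9.6-9.9, a first crossing at 10.6 is a rise of only 10.6 − 9.9 = 0.7 to 10.6 − 9.6 = 1.0, which is not a response. This is true and already included in the simulations. The net response among 9.0-9.9 starters is still inflated at SD 0.2-0.3.

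**The comparison of diagnoses.** A reader might also infer that the bias materially shrinks a true difference between iron deficiency anemia and anemia of chronic disease. That is not supported. With assumed 2-week rises of 0.6 and 1.1 and SD 0.3, a 33-point true difference in target attainment showed as 29. A second run gave 28 points observed, against 34 in true week-4 Hb without stopping but 27 in true Hb at stopping, so even the direction depends on how truth is defined. For scale, with 25 women per group and rates of 50% and 80%, the standard error is √(0.25/25 + 0.16/25) = 0.13, or 13 points.

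**Conclusion.** The concern holds in a limited form. As written, the plan allows an unconfirmed first crossing to serve as stopping trigger, target attainment and end value of the rise, and nothing in the analysis corrects for this.

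The firm part is the error at the end in women stopped at target. It barely changes with the assumed source population but depends on within-woman SD, which the plan does not give. The error at entry may be negligible. The >1.0 response is inflated mainly in 9.0-9.9 starters and little in 8.0-8.9 starters.

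The consequence is an overstated efficacy within each group, with no sound basis for claiming a distorted comparison between diagnoses. All sizes come from a simulation without the rhEPO add-on that 13 of the 33 iron-only starters received, so they indicate scale and are not estimates for this trial.

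Separately, the target (at least 10.5) and the stopping level (above 10.5) differ: a reading of exactly 10.5 attains the target but does not stop therapy. The two passages must be reconciled.

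**What to change.** Change the analysis only.

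1. **Define the readings.** State which count is the baseline and which is the end value.
2. **Main efficacy measure.** Estimate the Hb rise from all twice-weekly on-treatment counts in a linear mixed model with random intercept and slope per woman, starting Hb as a covariate (not as the first outcome point), and diagnosis-by-time as the contrast between the two anemia groups. Add rhEPO as a time-varying term only if the data support it, since 50 women will not carry an elaborate model. Because the stop depends on recorded Hb, likelihood estimates that use all those counts remain valid under it if the model is adequate. The simulations checked the mean slope only, not the classification of individual women and not the rhEPO term.
3. **Target attainment and the >1.0 response.** Do not score them on the triggering count. Use the next scheduled count where one exists. This does not remove the entry error from the >1.0 response: at SD 0.3 it still gave 40% against 31% true, which is why the model-based rise should lead.
4. **Reconcile** the target and the stopping level.

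The cost is some SAP text, a little more analysis of counts already collected, and possibly one more routine count after stopping. Reported response and target rates will look less favourable.

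### Women starting at Hb 9.6-9.9 g/dl can be stopped at target (Hb >10.5) and still be labelled insufficient responders, because sufficient response needs a rise >1.0 g/dl

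*Combined protocol and SAP*

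**What the plan says.** Entry Hb is 8.0 to 9.9 g/dl (Study population and criteria). The Therapy protocol section splits the 50 women by starting Hb: 17 at 8.0-8.9 received iron plus rhEPO from the start. For the others: "Patients with an Hb level between 9.0 and 9.9 g/dl (33 patients) received 200 mg iron sucrose" twice weekly.

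Three yardsticks of response then appear.

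- **Early response**, which decides whether rhEPO is added: "If response to therapy was poor (i.e. Hb increase <0.7 g/dl) after 2 weeks (13 patients), patients additionally received rhEPO". The stated basis is: "This cut-off for adequate primary response we choose on the basis of our previous experience".
- **Overall response**: "Sufficient overall response to therapy (the difference of baseline hemoglobin and after therapy) was defined as Hb increase >1.0 g/dl". No time is fixed for the Hb after therapy.
- **Target Hb**, which ends treatment: "therapy was stopped if the maximal iron sucrose dose was administered, or target Hb > 10.5 g/dl was achieved". The maximum dose is 1,600 mg. Under Study population and criteria, "Secondary endpoint was the target hemoglobin", there given as >=10.5 rather than >10.5.

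On the primary endpoint the plan says: "Primary endpoint was the assessment and comparison of the efficacy of anemia treatment", between the two diagnoses. It names no variable. The Statistical analysis section names tests for one purpose only: "Baseline characteristics were compared using Mann-Whitney and Chi-square tests when appropriate".

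**The concern.** For women who start near the top of the entry range, reaching target ends treatment before the overall-response criterion need be met. No clause counts a target stop as a response, and none continues treatment until the rise exceeds 1.0 g/dl. A woman going from 9.9 to 10.6 g/dl by week 2 is not a poor early responder (0.7 is not below 0.7) and has reached target, yet her overall response is not sufficient.

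Target Hb is assigned to the secondary endpoint and the 0.7 cut-off to the rhEPO decision. That leaves sufficient overall response as a likely measure for the primary comparison, although this is an inference. If it is used, two women gaining Hb at the same rate can be classified differently only because one started higher. The plan describes no adjustment for baseline Hb, so any difference in starting Hb between the diagnoses would carry into the response rates.

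**Working it through.** **Threshold arithmetic.** The inputs are the entry range, the stopping rule and the response definition above. Recording Hb to 0.1 g/dl is an assumption. The lowest Hb that triggers a target stop is 10.6, and the rise there is 10.6 minus starting Hb.

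| Starting Hb | Rise at 10.6 | Rise >1.0? | Stopping Hb at target but insufficient |
|---|---|---|---|
| 9.5 | 1.1 | yes | none |
| 9.6 | 1.0 | no | 10.6 |
| 9.7 | 0.9 | no | 10.6-10.7 |
| 9.8 | 0.8 | no | 10.6-10.8 |
| 9.9 | 0.7 | no | 10.6-10.9 |

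From 9.5 or below, every target stop meets the criterion. If treatment stopped at >=10.5, the affected starts would be 9.5-9.9 (rise at 10.5: 1.0 to 0.6). With Hb to two decimals and the >10.5 rule, the range begins at 9.51. All affected women lie in the 33-woman stratum (33 + 17 = 50).

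**Illustration of size.** The plan gives no response figure to reproduce, so this is a simulation under assumptions: starting Hb even over 9.0, 9.1, ..., 9.9; weekly gain Normal with SD 0.2, cut at 0; count-to-count SD 0.2; counts every 3.5 days; no rhEPO effect. Therapy stops at the first count >10.5 or at day 28 (1,600 / 200 = 8 doses; 8 / 2 per week = 4 weeks).

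*Which mean gain fits?* The plan reports 13 of 33 women (39%) with a rise <0.7 g/dl at 2 weeks. Mean gains of 0.4, 0.5, 0.6 and 0.8 g/dl per week give about 12, 7, 4 and under 1 such women. Of the gains tried (0.4 to 0.8), only 0.4 is consistent with the plan.

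At 0.4 g/dl per week:

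| Measure | Starts 9.0-9.5 | Starts 9.6-9.9 | Difference (points) |
|---|---|---|---|
| Rise >1.0 at stopping count | 75.8% | 31.4% | 44.4 |
| Rise >1.0 at next count after a target stop | 71.6% | 46.1% | 25.5 |
| Target reached | 66.7% | 86.4% | -19.7 |
| Rise >1.0 at stopping count, or target stop | 75.8% | 86.4% | -10.6 |

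The next-count row assumes that Hb keeps rising at the same rate after the stop.

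*At target but insufficient.* From 9.6 upward a rise >1.0 implies target, so the share at the stopping count is 86.4 - 31.4 = 55.0%. If starts were even, 33 x 0.4 = 13.2 women would start at 9.6-9.9, and 13.2 x 0.55 = 7.3 would be affected. At the next count the share is about 40%, or 13.2 x 0.40 = 5.3 women. The documents bound the number starting at 9.6-9.9 only between 0 and 33.

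*Carry-over to a comparison of diagnoses.* Within this stratum, each 10-point difference in the share starting at 9.6-9.9 would move response by 0.10 x 44.4 = 4.4 points (stopping count) or 0.10 x 25.5 = 2.6 points (next count), with no true difference.

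**The case against.** The strongest reply is that the yardsticks measure different things. The woman going from 9.9 to 10.6 is adequate at 2 weeks, at target and below a 1.0 rise, and all three can be true together. The plan never calls her a failure, and the secondary endpoint records her success. This stands against the tempting reading that the rules are logically contradictory or that the trial counts such women as failures in its primary analysis. It does not remove the problem that one rule ends treatment before the other need be satisfied.

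Second, the link to the primary endpoint is inferred. If efficacy were compared as continuous Hb change or as target attainment, the 1.0 cut-off would not enter. This stands, so the consequence is conditional.

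Third, the size depends on when the Hb after therapy is taken. The plan fixes no time, and it refers for its treatment scheme to a source outside these documents. Overshoot is already in the stopping-count figures, and a later rise narrows the gap, as the next-count row shows. Count-to-count variation also matters: with none, the gaps over mean gains of 0.4-0.8 are 61-70 points (stopping count) and 5-19 points (next count).

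Fourth, the simulation omits any rhEPO effect, although the 13 poor early responders received it, and omits the 17 women starting at 8.0-8.9. Both limits stand.

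Finally, the text is in the past tense with observed counts, so changing the response definition would be a redefinition after treatment. That is a reason to show both definitions.

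**Conclusion.** The mismatch is exact. With Hb to 0.1 g/dl and the >10.5 stop, 4 of the 10 starting values in the 9.0-9.9 stratum are affected (5 of 10 under >=10.5). Women starting there can be stopped at target and labelled insufficient unless Hb overshoots or keeps rising. Nothing in the documents resolves this.

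The effect on the primary comparison is conditional on the response label being used for it. In the setting that fits the reported early-response count, the label separates higher from lower starters by about 44 points at the stopping count or 26 at the next count. These figures illustrate the mechanism and do not estimate this trial's results. Faster gains give stopping-count gaps up to 53 points and response near 100% for lower starters, but they are incompatible with 13 of 33 poor early responders.

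A reader might infer that the comparison of diagnoses is biased. The documents do not show that: starting Hb by diagnosis is not given, so a bias is possible but its size and direction are unknown. The point merits correction because the remedy is cheap.

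**What to change.** 1. Use one target, either >10.5 or >=10.5, in both the endpoint and the stopping rule.
2. Count a woman as a sufficient responder if her Hb rise is >1.0 g/dl or therapy stopped because target was reached. Show the result under the plan's >1.0 definition as well.
3. Compare the diagnoses on Hb rise adjusted for baseline Hb, and report target attainment alongside. The continuous rise is the safer place for the covariate: under the revised rule the illustration leaves about 6.6 non-responders among 33 women at 0.4 g/dl per week (33 x [0.6 x 24.2% + 0.4 x 13.6%]), which may be too few for a baseline-adjusted binary model.

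The cost is one clause, one covariate and a few extra lines of reporting. Doses, visits, counts and treatment are unchanged, and baseline Hb is already collected. The downside is that rises of about 0.7-1.0 g/dl count as success when they reach target (from 0.6 if the target is >=10.5), and the response measure then overlaps the secondary endpoint. The revised rule also leaves a gap of about 11 points in the opposite direction, because target is nearer for women who start higher. Reporting the baseline-adjusted rise keeps both effects visible.

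### Stopping therapy at a common Hb target attenuates the IDA versus ACD difference in end-of-therapy Hb rise, the only whole-course efficacy measure the plan defines

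*Combined protocol and SAP*

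**What the plan says.** Study population and criteria: "Primary endpoint was the assessment and comparison of the efficacy of anemia treatment in pregnant women with iron deficiency anemia and anemia of chronic disease" (the ACD group being women who are also truly iron deficient). No variable, time point or test is attached to that comparison. The same section adds "Secondary endpoint was the target hemoglobin", set at 10.5 g/dl or more.

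Therapy protocol: "Sufficient overall response to therapy (the difference of baseline hemoglobin and after therapy) was defined as Hb increase >1.0 g/dl". This is the only response measure that covers the whole course. A separate check at 2 weeks (rise below 0.7 g/dl) decides whether women who started on iron alone also receive rhEPO; 13 of 33 did. On the end of treatment: "The maximum total iron dose was 1,600 mg", and "therapy was stopped if the maximal iron sucrose dose was administered, or target Hb > 10.5 g/dl was achieved".

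Number of infusions, total iron used and time to target are not listed as endpoints. Statistical analysis names tests for baseline characteristics only.

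**The concern.** The end of therapy is not a fixed time here. It is the moment when Hb passes the target or the iron allowance runs out. A fast responder is stopped early, at a value just above 10.5 g/dl. A slower responder goes on receiving infusions and, if she gets there, stops at much the same value. From the same baseline, the two record nearly the same rise although one needed more treatment.

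The primary question is whether treatment works differently in IDA and ACD. Because the primary endpoint names no variable, reading efficacy as the end-of-therapy rise is an inference, but it is the best supported one. If the question is answered that way, a real difference in response is shrunk by the way treatment is stopped, and a finding of similar efficacy would be weak evidence.

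**Working it through.** The documents state no effect size, SD or power, so there is no figure of the plan's own to reproduce.

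**Inputs from Therapy protocol.** 200 mg iron twice weekly in the 9.0-9.9 g/dl stratum (33 women); iron plus rhEPO from the start in the 8.0-8.9 stratum (17 women, iron amount per dose not given, 200 mg assumed); cap 1,600 mg; stop above 10.5 g/dl; rhEPO added if the 2-week rise is below 0.7 g/dl (13/33 = 39.4%).

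**1. Length of the course.** 1,600/200 = 8 infusions; 8/2 = 4 weeks.

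**2. Rise at the stop, and rate needed to get there.** The rise at target is just over 10.5 minus baseline. The rate needed to reach target within the cap is that rise divided by 4.

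| Baseline (g/dl) | Rise at target (g/dl) | Rate needed (g/dl per week) |
|---|---|---|
| 9.9 | 0.6 | 0.15 |
| 9.5 | 1.0 | 0.25 |
| 9.0 | 1.5 | 0.375 |
| 8.0 | 2.5 | 0.625 |

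Among women who reach target, response speed hardly enters the rise. Women slower than the last column stop short, and their shortfall stays visible.

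**3. Noise-free example (assumed rates).** Baselines 9.0, 9.1, ..., 9.9 in equal shares; group A rises 0.50 and group B 0.35 g/dl per week, so 0.25 and 0.175 per infusion.
- Fixed 4 weeks on continued dosing: 4 x (0.50 - 0.35) = 0.60 g/dl difference.
- Under the stop rule: A uses 4.8 infusions on average, rise 4.8 x 0.25 = 1.20; B uses 6.4, rise 6.4 x 0.175 = 1.12. Difference 0.08 g/dl.
- Target reached: 100% of A and 80% of B.

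**4. Same mean rates with variation** (assumed slope SD 0.1 g/dl per week, reading SD 0.2 g/dl). The 0.60 g/dl difference falls to about 0.13 in the iron-start stratum (0.13/0.60 = 22% kept). In the full mix of both strata with no rhEPO effect it falls to about 0.26 (43% kept), and further if rhEPO has an effect.

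**5. Whole algorithm, tuned to the 13/33 poor responders.** Assumed: linear slopes, slope SD 0.10-0.25, IDA-ACD slope difference 0.1-0.3 and rhEPO effect 0-0.3 (all in g/dl per week), reading SD 0.2 g/dl, same baseline mix in both groups. The benchmark is the same treatment, including the rhEPO add-on, read at a fixed 4 weeks.
- The end-of-therapy rise keeps 17% to 52% of the difference, so 48% to 83% is lost: about half if rhEPO adds nothing, 72% to 83% if it adds 0.3.
- Example (slope SD 0.15, slope difference 0.2, rhEPO effect 0.15): 0.72 g/dl at fixed 4 weeks, 0.27 under the stop rule; infusions 5.4 vs 6.7; target reached 91% vs 61%; rise above 1.0 g/dl in 84% vs 70%.
- With a slower mean slope (0.30 g/dl per week, not tuned to 13/33) the rise keeps 38% to 67%, so 33% to 62% is lost.

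**6. Which outcome shows the difference best?** Standardised differences between groups:
- 2-week rise: 0.74 to 1.12 across the scenarios run, against 0.09 to 0.91 for the end-of-therapy rise, and larger in every one.
- Infusions against end-of-therapy rise at the rates in step 4: 0.80 vs 0.46 in the iron-start stratum (0.78 vs 0.42 in a repeat run); in the full mix 0.55 vs 0.61 if rhEPO adds nothing, and 0.65 vs 0.28 if it adds 0.15 g/dl per week.

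**The case against.** The strongest defence is that the plan does not lose the difference altogether. The sentence that stops therapy at target also stops it at 1,600 mg, so slow responders end with a smaller rise. The secondary endpoint also picks up part of the signal: in the tuned runs the share reaching target differs by about 8 to 51 percentage points. The plan already has a fixed-time reading, the 2-week check. All of this stands, and it limits the size of the point.

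A reader might infer that the rule equalises the outcome. The documents do not support that: the cap prevents it, and how much is lost depends on response speeds and an rhEPO effect that they do not give.

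A reader might also infer that the responder rate can reverse, because the noise-free example gives a rise above 1.0 g/dl in 60% of A and 70% of B. That is a rounding artefact. The groups differ at one baseline of ten, 9.6, where A stops at a rise of exactly 1.00 and B at 1.05. With the variation in step 4 the order is right, at about 74% vs 62%.

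The example cannot be taken as free of the rhEPO step-up either. Group B's 2-week rise is 2 x 0.35 = 0.70, exactly on the cut-off, so with variation about half of B would be stepped up.

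Finally, infusion count is not always the more sensitive outcome, as step 6 shows. That argues for pairing it with the 2-week rise, and against discarding the end-of-therapy rise.

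**Conclusion.** The point holds as attenuation. In women who reach target, the end-of-therapy rise mainly reflects baseline Hb, so the stop rule hides part of a true IDA versus ACD difference, and no listed endpoint measures the infusions or time needed. Under the assumed slopes the loss is roughly a third to more than four-fifths. The mechanism follows from the plan's own rules; the size does not, because the slopes, their spread, the rhEPO effect, the IDA/ACD split and the dose per infusion in the 8.0-8.9 stratum are all assumed. The practical consequence is that similarity on the end-of-therapy rise, or on the rate above 1.0 g/dl, cannot by itself support a claim of equal efficacy.

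**What to change.** Leave dosing and stopping as they are and name the outcomes for the primary comparison:

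- **Hb rise at the common 2-week visit.** In the iron-start stratum this precedes any rhEPO step-up. State how women who reach target before 2 weeks are handled: in the noise-free example, group A women starting at 9.8 or 9.9 stop after 3 infusions, at 1.5 weeks.
- **Infusions or time from first dose to first Hb above target**, with women who exhaust 1,600 mg counted as not having reached it.

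Analyse both within, or adjusted for, starting-Hb stratum (8.0-8.9 vs 9.0-9.9 g/dl), since the strata start on different treatment. Keep the end-of-therapy rise and the rate above 1.0 g/dl as descriptive results, with a statement that similarity on them alone is not evidence of equal efficacy.

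The target is written as 10.5 g/dl or more in Study population and criteria and as above 10.5 g/dl in Therapy protocol. These passages must be reconciled, because the time-to-target outcome depends on the definition.

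Cost: wording and a little more analysis. Laboratory assessment already has the blood values checked twice a week. The small downside is a result stated partly in doses or time instead of g/dl.
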